2.3.1 Original Text

Section 6.11.2 Primary Efficacy Analysis

A one-tailed restricted maximum likelihood (REML)-based mixed model for repeated measures (MMRM) with one sided 95% CI will be utilized to assess the difference between treatment groups with respect to change from baseline to Week 12 in the weekly mean of the NRS score assessing average pain intensity in the past 24 hours.

2.3.2 New Text

Section 6.11.2 Primary Efficacy Analysis

A one-tailed restricted maximum likelihood (REML)-based mixed model for repeated measures (MMRM) with one sided 95% CI will be utilized to assess the difference between treatment groups with respect to change from baseline to Week 12 in the weekly mean of the NRS score assessing average pain intensity in the past 24 hours. Baseline Observation Carried Forward (BLOCF) imputation (based on Section 6.11.1.1) will be used to impute data for subjects discontinuing the study drug due to an AE or lack of efficacy prior to Week 12.

2.4 Change 4

2.4.1 Original Text

Section 6.11.3.1 Pattern-Mixture Model

To assess the robustness of the results to deviations from the MAR assumption in the primary analysis, a sensitivity analysis will be conducted such that non-monotone missing data will be imputed under a missing at random (MAR) assumption while the monotone missing data will be imputed under a missing not at random (MNAR) assumption (i.e., that missingness is also dependent on the unobserved variable values).

2.4.2 New Text

Section 6.11.3.1 Pattern-Mixture Model

To assess the robustness of the results to deviations from the MAR assumption in the primary analysis, a sensitivity analysis will be conducted such that non-monotone missing data will be imputed under a missing at random (MAR) assumption while the monotone missing data and data occurring after an ICE will be imputed under a missing not at random

(MNAR) assumption (i.e., that missingness is also dependent on the unobserved variable values).

2.5 Change 5

2.5.1 Original Text

Section 6.11.3.2 Tipping Point Analysis

If the primary efficacy analysis in Section 6.11.2 significantly favors any NYX-2925 treatment group, a tipping point sensitivity analysis⁴ for the primary efficacy endpoint will be conducted to investigate how severe the departure from the MAR assumption data must be to overturn conclusion from the primary analysis.

In this analysis, the assumption will be that that missing data in the NYX-2925 groups follows a MNAR pattern. A tipping point-based approach will be used such that the trajectories of the subjects in the NYX-2925 groups after early withdrawal are assumed to be worse than placebo by a fixed amount (δ). The value of δ is the adjustment added during imputation to the change from baseline NRS scores at each visit after study discontinuation. This increment is added only to the imputed change from baseline NRS scores at visits after study discontinuation of the subjects in NYX-2925. The value of δ will increase in increments of 0.5 (i.e., 1.0, 1.5, 2.0) up to the point at which the treatment difference at Week 12 is no longer statistically significant. This analysis provides a measure of the degree by which the subjects in the NYX-2925 groups who discontinued early would need to be worse (compared to those who did not discontinue) at each post-discontinuation visit in order for the null hypothesis of no treatment difference to no longer be rejected. Intercurrent events will be imputed by BLOCF as estimand in Section 6.11.1.1. Each imputed dataset produced through PROC MI procedure will be processed as follows.

2.5.2 New Text

Section 6.11.3.2 Tipping Point Analysis

If the primary efficacy analysis in Section 6.11.2 significantly favors any NYX-2925 treatment group, a tipping point sensitivity analysis⁴ for the primary efficacy endpoint will be conducted to investigate how severe the departure from the MAR assumption data must be to overturn conclusion from the primary analysis.

In this analysis, the assumption will be that that missing data and data occurring after an ICE in the NYX-2925 groups follows a MNAR pattern. A tipping point-based approach will be used such that the trajectories of the subjects in the NYX-2925 groups after early withdrawal

are assumed to be worse than placebo by a fixed amount (δ). The value of δ is the adjustment added during imputation to the change from baseline NRS scores at each visit after study discontinuation. This increment is added only to the imputed change from baseline NRS scores at visits after study discontinuation of the subjects in NYX-2925. The value of δ will increase in increments of 0.5 (i.e., 1.0, 1.5, 2.0) up to the point at which the treatment difference at Week 12 is no longer statistically significant. This analysis provides a measure of the degree by which the subjects in the NYX-2925 groups who discontinued early would need to be worse (compared to those who did not discontinue) at each post-discontinuation visit in order for the null hypothesis of no treatment difference to no longer be rejected. Each imputed dataset produced through PROC MI procedure will be processed as follow.

2.6 Change 6

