12.6.2. Sensitivity Analysis

As a sensitivity analysis for the primary efficacy endpoint, an analysis of covariance (ANCOVA) model will be used to assess treatment differences. The model will include factors for study site and treatment and include the baseline value of the response variable as a covariate.

Sensitivity analyses will be performed on the primary endpoint, evaluating the impact of the missing at random (MAR) assumption for missing data. Multiple imputation (MI) techniques based on Pattern Mixture Models (PMM) will be applied as the first sensitivity analysis. This methodology will structure data based on a missingness pattern having a monotone structure. An MI analysis with missing not at random (MNAR) assumption will be applied as the second sensitivity analysis. Placebo group based imputation will be used (i.e. the trajectories of the subjects with missing data on NYX-2925 are assumed to follow the placebo group after discontinuation).

If the primary efficacy analysis significantly favors one or both doses of NYX-2925, a tipping point sensitivity analysis for the primary efficacy endpoint will be conducted. In this analysis, the assumption will be that that data in the NYX-2925 groups are not missing at random. A tipping point based assumption will be used, i.e. the trajectories of the subjects in each of the NYX-2925 groups after withdrawal are assumed to be worse than placebo by an amount of delta.

Successively harsher deltas will be imposed on the subjects in the NYX-2925 groups, starting with a mean weekly NRS score increment (increase) of 0.5 points. The delta will be further increased in steps of 0.5 points (i.e., 1.0, 1.5, 2.0) until the statistical significance is lost, i.e. until the p-value becomes >0.05 .

[figure not shown]

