6.11.3.2 Tipping Point Analysis

If the primary efficacy analysis in Section 6.11.2 significantly favors any NYX-2925 treatment group, a tipping point sensitivity analysis⁴ for the primary efficacy endpoint will be conducted to investigate how severe the departure from the MAR assumption data must be to overturn conclusion from the primary analysis.

In this analysis, the assumption will be that that missing data in the NYX-2925 groups follows a MNAR pattern. A tipping point-based approach will be used such that the trajectories of the subjects in the NYX-2925 groups after early withdrawal are assumed to be worse than placebo by a fixed amount (δ). The value of δ is the adjustment added during imputation to the change from baseline NRS scores at each visit after study discontinuation. This increment is added only to the imputed change from baseline NRS scores at visits after study discontinuation of the subjects in NYX-2925. The value of δ will increase in increments of 0.5 (i.e., 1.0, 1.5, 2.0) up to the point at which the treatment difference at Week 12 is no longer statistically significant. This analysis provides a measure of the degree by which the subjects in the NYX-2925 groups who discontinued early would need to be worse (compared to those who did not discontinue) at each post-discontinuation visit in order for the null hypothesis of no treatment difference to no longer be rejected. Intercurrent events will be imputed by BLOCF as estimand in Section 6.11.1.1. Each imputed dataset produced through PROC MI procedure will be processed as follows:

- All values imputed for the placebo group will remain unchanged
- All values imputed for the NYX-2925 groups will be incremented by a value of δ , which will vary from 0 up to a value by which statistical significance is not reached
- The modified data will be analyzed using similar analysis as described in Section 6.11.2.

Results will then be combined using PROC MIANALYZE and will consequently be recorded

The “tipping point” is defined as the value of δ at which the result changes from a statistically significant treatment effect to a treatment effect that is no longer statistically significant. The larger the value of δ , the more robust the conclusion from the primary analysis with respect to assumptions around missing data.

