1. BACKGROUND

This document details changes and / or additions to the planned statistical analyses for Aptinyx Inc, protocol NYX-2925-2005 study titled “A Randomized, Double-Blind, Placebo-Controlled Study to Assess the Efficacy and Safety of NYX-2925 in Subjects with Fibromyalgia” previously described in V1.0 of the Statistical Analysis Plan (SAP) dated 21-JUL-2022.

These amendments were made post database lock and after the study was unblinded.

Rationale for Addendum:

- 1) To detail the Baseline Observation Carried Forward (BLOCF) imputation used in primary efficacy analysis
- 2) To update the definition of prior medication
- 3) To update the title of outputs:

Output Number and Title	Requested Change
Table 14.2.2.2.1 Patient Global Impression of Change, Change from Baseline to until Week 12, Mixed Model for Repeated Measures – 1-Sided Test – Modified Intent-to-Treat Population	Change the title to ‘Patient Global Impression of Change by Visit, Mixed Model for Repeated Measures – 1-Sided Test – Modified Intent-to-Treat Population’
Table 14.2.2.2.2 Patient Global Impression of Change, Change from Baseline to until Week 12, Mixed Model for Repeated Measures – 2-Sided Test – Modified Intent-to-Treat Population	Change the title to ‘Patient Global Impression of Change by Visit, Mixed Model for Repeated Measures – 2-Sided Test – Modified Intent-to-Treat Population’

In addition to the above changes and / or additions, a number of minor changes have been made to the shells so that they reflect the presentation of the final set of tables, figures and listings (TFLs). These changes have not been detailed here.

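### After unblinding, the addendum dropped the BLOCF rule from the tipping-point analysis without a stated reason, so the analysis now varies the intercurrent-event rule together with the missing-data assumption

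*SAP*

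**What the plan says.** SAP V1.0, section 6.11.3.2, gives the purpose of the tipping point: to find how far from missing at random (MAR) the data must lie before the primary conclusion fails. It then fixes the ICE rule: "Intercurrent events will be imputed by BLOCF as estimand in Section 6.11.1.1". Two processing rules follow: "All values imputed for the NYX-2925 groups will be incremented by a value of" delta, with delta running upward from 0, and "All values imputed for the placebo group will remain unchanged".

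Addendum 2.5.2 rewrites the section without the BLOCF sentence and assumes that "missing data and data occurring after an ICE in the NYX-2925 groups follows a MNAR pattern". It does not say what happens to placebo data after an ICE, and it leaves the processing rules as they were. It keeps the condition for running the analysis: "If the primary efficacy analysis in Section 6.11.2 significantly favors any NYX-2925 treatment group".

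On timing, the addendum's Background says "These amendments were made post database lock and after the study was unblinded". Of its three reasons, the only one that touches BLOCF is "To detail the Baseline Observation Carried Forward (BLOCF) imputation used in primary efficacy analysis"; the others concern prior medication and output titles.

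Other addendum changes bear on the same rule:
- 2.2.2 limits BLOCF to the primary efficacy analysis, and 2.3.2 restates it there.
- 2.4.2 puts post-ICE data under missing not at random (MNAR) in the pattern-mixture model.
- 2.6.2 and 2.7.2 specify no imputation for the ANCOVA and the pooled MMRM.

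Protocol 12.6.2 describes NYX-2925 trajectories that "after withdrawal are assumed to be worse than placebo by an amount of delta". It makes no exception for baseline-carried-forward values and starts delta at 0.5.

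**The concern.** A tipping point is easiest to interpret when one thing moves. Under V1.0 the ICE rule matched the primary analysis and the imputation of the other missing data was varied. Under the addendum, subjects on NYX-2925 who stop for an adverse event or lack of efficacy leave zero change and move to a placebo-based trajectory plus delta. A difference from the primary result can then come from the ICE rule, from departure from MAR, or from both, and the output cannot separate them.

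The change was made with treatment codes known and without an explanation, so a reader cannot check that it was independent of the results. No other mean-change analysis fills the gap. The pattern-mixture model also moves post-ICE data to MNAR, and the ANCOVA and pooled MMRM drop the imputation.

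**Working it through.** **1. The ICE rule, analysis by analysis**

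| Analysis | SAP V1.0 | Addendum |
|---|---|---|
| Primary MMRM | BLOCF | BLOCF |
| Tipping point | BLOCF, stated | NYX-2925: MNAR plus delta; placebo not stated |
| Pattern-mixture | BLOCF not stated | MNAR |
| ANCOVA | BLOCF not stated | no imputation |
| Pooled MMRM | repeats the primary model | no imputation |

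After the addendum, no row below the first keeps the primary ICE rule.

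**2. Planning scale.** SAP section 4 gives 85 per arm, SD 1.7, difference 0.73, one-sided 0.05 and about 88% power. SE = 1.7 × sqrt(2/85) = 0.261. A two-sample power calculation gives 0.876, which reproduces the 88%. The SE serves below only as a yardstick.

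**3. Closed form at delta = 0.** Assumptions, not in the documents: placebo mean change m = -1 to -2; effect d = -0.73 in subjects without an ICE; ICE rates pA (active) and pP (placebo) of 5% to 15%; no other missing data.
- BLOCF estimate: (1 - pA)(m + d) - (1 - pP)m.
- Addendum estimate, with all post-ICE values at the placebo mean: (1 - pA)d.
- Gap (first minus second): (pP - pA)m. A positive gap means the addendum's starting point looks better for the drug.

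Results: 0 at equal rates; +0.10 (m = -1) to +0.20 (m = -2) at 15% active and 5% placebo; -0.10 to -0.20 at 5% and 15%.

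**4. Regression-based imputation at delta = 0.** A simulation imputed Week 12 from Weeks 1 to 4, with the regression fitted in placebo subjects without an ICE. It used 200,000 subjects per arm and SD 1.7. Correlation was compound-symmetric at 0.6 or 0.8, or autoregressive with 0.6 or 0.8 at four weeks. Onset was plateau or linear. ICEs came after Week 4, either unrelated to response or more likely with a worse Week 4 change. With placebo imputed the same way, the gap was:
- equal rates of 5%, 10% or 15%: 0.00 to +0.07 (at most 0.07/0.26 = 0.27 SE);
- 15% active, 5% placebo: +0.03 to +0.27 (about 1 SE at the top);
- 5% active, 15% placebo: -0.20 to +0.01.

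**5. Direction as delta grows.** In the setting of step 3, hold BLOCF values without delta in the V1.0 run. The addendum estimate minus the V1.0 estimate is then (pA - pP)m + pA × delta; positive means the addendum is harsher on the drug.
- Equal 10% rates, delta = 1: +0.10.
- 15%/5%: -0.10 + 0.15 × delta for m = -1, which crosses zero at delta = 0.67; -0.20 + 0.15 × delta for m = -2, which crosses at 1.33.
- 5%/15%: positive at every delta.

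If V1.0 meant BLOCF values to receive delta too, the difference is (pA - pP)m at every delta. Neither version is uniformly the lenient one.

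**6. Separate V1.0 code error (SAP 6.11.3.1).** The sample code keeps same-week rows through `WEEK=_WEEK`, but runs MIANALYZE on DIFFS `BY TREATMENT` only. It therefore combines 12 weeks, rows from two LSMEANS statements and, for one dose (depending on level order), the dose-versus-dose contrast. It treats 12 × 20 × 2 = 480 rows as imputations instead of 20, and 960 for the dose with two contrasts. A Week 12 effect of -0.73 reached linearly averages to -0.73 × 6.5/12 = -0.395. With a linear rise to a plateau at Week 4 it is -0.73 × 10.5/12 = -0.639. With equal doses, these halve for the dose that also carries the dose-versus-dose rows. The LSMEANS step runs by treatment and week, so there only the duplicates matter (40 rows instead of 20).

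**The case against.** The strongest reply is that the new form fits the protocol better than V1.0 did. Protocol 12.6.2 applies delta after withdrawal with no BLOCF exception. Letting delta act on subjects who stopped for an adverse event or lack of efficacy is a legitimate stress test; one reading of V1.0 froze them at zero change. The addendum's edits also consistently place BLOCF in the primary analysis, so this deletion is not isolated. The analysis runs only if a dose is significant, and the primary analysis is untouched. All of this stands and limits the weight of the point. It does not supply a reason for removing a prespecified rule after unblinding, nor an analysis that isolates the MAR assumption.

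The comparison at delta = 0 should not be pressed too far. The protocol starts at 0.5, and only the SAP processing rule starts at 0. Even under V1.0, delta = 0 did not reproduce the primary analysis for missing data without an ICE, because trajectories after withdrawal were referred to placebo. The defect is confined to the ICE rule.

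A reader might infer a gap as large as 0.37 points (0.37/0.26 = 1.4 SE). That figure arises only if placebo post-ICE data stay at BLOCF while NYX-2925 data do not. Addendum 2.5.2 does not say so, and 2.2.2, which confines BLOCF to the primary analysis, makes it unlikely.

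On the code: it is labelled as a sample, the text promises results by week, and SAP 6.3.3 requires independent programming by a statistician. The error may be caught in practice, but the written specification is still wrong.

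**Conclusion.** The point holds as a matter of text: a prespecified ICE rule was removed from the tipping point after unblinding, with no stated reason, and no remaining mean-change sensitivity or supportive analysis keeps that rule while relaxing MAR for the other missing data. The qualifier mean-change matters, because the responder endpoints have their own rules for missing data.

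The size cannot be fixed, because the documents give no ICE rates. It runs from negligible at equal rates to about one planning SE at an assumed 15%/5% imbalance, with either sign. These figures rest on the assumed placebo change, correlations and ICE timing, and on placebo data being imputed within placebo.

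A reader might infer that the change was made to help the drug, or that it breaches the protocol. The documents support neither. The direction depends on delta, the placebo change and the ICE rates, and the new form is compatible with Protocol 12.6.2. What can be said is that influence of the results cannot be excluded from the record as written. The primary estimate is not affected. The change below is worth making, but it bears on the robustness claim and only if a dose is significant.

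**What to change.** - Report the tipping point with BLOCF for post-ICE data in all arms as the prespecified version. State that V1.0 was ambiguous on whether BLOCF values receive delta, and that they are held without delta here so that only missing data not preceded by an ICE are varied. This is a choice between two readings and should be presented as one.
- Keep the addendum version as supplementary, labelled as specified after unblinding. Give the reason for the deletion and say how placebo post-ICE data are handled.
- Separately, in 6.11.3.1, output DIFFS from one LSMEANS statement, keep only contrasts against placebo within the same week, and sort and run MIANALYZE `BY TREATMENT _TREATMENT WEEK`. Remove the duplicates from the LSMEANS output as well.

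Cost: a few sentences, one extra run and table if a dose is significant, and a corrected combining step. The tipping delta may move either way, and two versions will need explaining side by side.

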2.6.1 Original Text

Section 6.11.3.3.1 Analysis of Covariance on change from baseline to Week 12 in the weekly mean of the NRS score assessing average pain intensity in the past 24 hours

To assess the robustness of the result observed for the primary endpoint, the one-sided Analysis of Covariance (ANCOVA) model with site and treatment as factors, and baseline NRS score as a covariate will be employed as a supportive analysis.

2.6.2 New Text

Section 6.11.3.3.1 Analysis of Covariance on change from baseline to Week 12 in the weekly mean of the NRS score assessing average pain intensity in the past 24 hours

To assess the robustness of the result observed for the primary endpoint, the one-sided Analysis of Covariance (ANCOVA) model with site and treatment as factors, and baseline NRS score as a covariate will be employed as a supportive analysis. No imputation will be performed ahead of performing this analysis.

2.7 Change 7

2.7.1 Original Text

Section 6.11.3.3.2 Pooled Analysis

To provide supportive evidence for the primary objective, a pooled analysis will be performed where the NYX-2925 50 mg group will be pooled with the NYX-2925 100 mg group and compared against the placebo group. The REML-based MMRM model in Section

6.11.2 will be repeated with site, treatment group (NYX-2925-treated group versus Placebo-treated group), week, baseline NRS score, and treatment-by-week interaction as terms in the model. A line plot showing the LS means and 95% CIs of the weekly mean NRS scores from Week 1 through Week 12 for pooled treatment group and placebo group will be presented.

2.7.2 New Text

Section 6.11.3.3.2 Pooled Analysis

To provide supportive evidence for the primary objective, a pooled analysis will be performed where the NYX-2925 50 mg group will be pooled with the NYX-2925 100 mg group and compared against the placebo group. The REML-based MMRM model in Section 6.11.2 will be repeated with site, treatment group (NYX-2925-treated group versus Placebo-treated group), week, baseline NRS score, and treatment-by-week interaction as terms in the model. No imputation will be performed ahead of performing this analysis. A line plot showing the LS means and 95% CIs of the weekly mean NRS scores from Week 1 through Week 12 for pooled treatment group and placebo group will be presented.

2.8 Change 8

2.8.1 Original Text

Section 6.11.3.4 Exploratory Analyses

Potential moderators of treatment outcome will be explored. An MMRM model will be performed in a similar manner to the primary analysis, as described in Section 6.11.2, with fixed effects for site, sex, treatment group, week, baseline NRS score, and treatment-by-week interaction. Fixed effect terms for baseline variable of interest and treatment-by-baseline variable interaction will also be added to the model as follows (one model per point).

2.8.2 New Text

Section 6.11.3.3 Exploratory Analyses

[figure not shown]
[figure not shown]
Potential moderators of treatment outcome will be explored. An MMRM model will be performed in a similar manner to the primary analysis, as described in Section 6.11.2, with fixed effects for site, sex, treatment group, week, baseline NRS score, and treatment-by-week interaction. Fixed effect terms for baseline variable of interest and treatment-by-

baseline variable interaction will also be added to the model as follows (one model per point). No imputation will be performed ahead of performing these exploratory analyses.

Approval for implementation of

Statistical Analysis Plan Post Database Lock Addendum

REVIEW / APPROVAL SIGNATURES

Plan Author   	Plan Reviewer   
Plan Approver ,   	Plan Approver ,
